Sample size estimates are based on a marginal test of metformin versus placebo comparison, controlling for fluvoxamine and ivermectin use, and selected to provide at least 80% power with

5% two-sided type I error rate for the target effect indicated by the event rates in the above figure and described in detail in subsection 12.3.1. The sample size estimates are also inflated by 11% and rounded to account for interim analysis plan (see subsection 13.4) and study withdrawals.

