# Factorial design maximizes the use of placebo

Each patient gets 2 types of pills		Metformin (n=563)	Placebo (n=187)	
	Fluvoxamine (n = 375)	Metformin / Fluvoxamine n =188 6% event rate if both effective	Fluvoxamine / placebo n=187 11% event rate	
	Ivermectin (n=375)	Metformin/Ivermectin n = 188 6% event rate if both effective	Ivermectin/Placebo n = 187 11% event rate	
		Metformin / placebo n = 187 11% event rate	Placebo / Placebo n=187 20% event rate	
	Total	563	561	

[figure not shown]
• If two medications are effective, we will have 80% power to detect a difference over placebo.

• If only one medication is effective, we will have 90% power to detect a difference over placebo.

• Assumes a 10% loss to follow-up rate.

These considerations result in a planned enrollment of 1,124 participants (187-188 in each arm). Because these sample size calculations are based on marginal tests, the actual power may be higher when based on the planned tests using adjusted logistic regression models adjusted for various predictive factors as described later.

VERSION 3.4

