#### $H_0: \pi_T \ge \pi_C$ versus $H_A: \pi_T < \pi_C$

The hypothesized marginal rate of the primary endpoint under placebo is 20%. The expected event rate for the primary outcome in the single medication treatment arms is 11% which corresponds to a relative risk reduction of 45%. To detect this effect with 80% power using a marginal test with 5% two-sided type I error requires 337 participants in each comparison group. To account for effects of other drugs used in combination, which may reduce the event rate of the control group, for the interim analysis plan, and for losses to follow-up, we plan to enroll 1,124 participants in total.

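### The 11% inflation is fully used by the 10% loss to follow-up, so nothing covers the interim analyses, and the quoted 80% and 90% are single-look powers for fluvoxamine or ivermectin, not metformin

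*Protocol*

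**What the plan says.** Section 12.3 names the basis of the calculation: "Sample size estimates are based on a marginal test of metformin versus placebo comparison". The other two drugs are adjusted for, and the target is a power of 80% or more at a two-sided 5% level. A later sentence reads: "The sample size estimates are also inflated by 11% and rounded to account for interim analysis plan". It names withdrawals as the second reason.

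The factorial table in the same section gives arms of 187 or 188, with event rates of 20% (double placebo), 11% (one drug) and 6% (two effective drugs). One of its notes reads "If two medications are effective, we will have 80% power to detect a difference over placebo". Another puts the figure at 90% when a single drug works. On losses the note is "Assumes a 10% loss to follow-up rate". The planned total is 1,124.

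Section 12.3.1 says that 337 per comparison group gives 80% power for 20% v 11%. It says that 1,124 allows for the effects of the other drugs, for the interim plan and for losses. Section 12.4.2 (Table 2) sets looks at 62, 386, 774 and 1,124, calls the futility boundary non-binding and calls the harm boundary binding. The overview in Section 5.1 and the text on prespecified analyses in Section 12.3.1 raise the total to 1,350 (225 per arm).

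**The concern.** One inflation factor is credited with two purposes. If a 10% loss needs all of it, the statement that the interim plan is allowed for is wrong, and the quoted powers describe a trial with a single final analysis rather than one with four looks.

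The reader also cannot tell which drug the 80% and 90% belong to. The text says metformin, but the metformin comparison uses all six arms and is much larger than 337 per group. At stake is whether the sample size section describes the design that is actually monitored. A reader who takes it at its word will credit the plan with an allowance it does not contain and will attach the powers to the wrong comparison.

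**Working it through.** **Inputs.** Two-sided 5%; event rates 20%, 11% and 6%; 337 per comparison group; 10% loss; total 1,124 (Sections 12.3 and 12.3.1). Efficacy boundaries 3.737 / 3.116 / 2.461 / 2.001, futility -2.130 / -0.093 / 1.087 / 2.001, harm -2.5 / -2.5 / -2.0 / -2.0 (Table 2).

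**1. The inflation.** 1/0.90 = 1.111. 337/0.90 = 374.4, so 375 per comparison group, which is the table's figure for fluvoxamine and for ivermectin. Three such pairs of arms: 3 x 337/0.90 = 1,123.3, against the stated 1,124. Loss alone reproduces the plan.

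**2. The plan's powers.** For fluvoxamine (ivermectin is the same), the marginal rates are:
- both it and metformin effective: (20 + 11)/2 = 15.5% v (11 + 6)/2 = 8.5%;
- only it effective: 20% v 11%.

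The fixed-design power is Φ[(d - 1.96 x SE0)/SE1], where d is the rate difference, SE0 the pooled and SE1 the unpooled standard error.
- 15.5% v 8.5%, n = 337: SE0 = √(2 x 0.12 x 0.88/337) = 0.02503; SE1 = √(0.20875/337) = 0.02489; (0.07 - 0.04907)/0.02489 = 0.841; power 80.0%.
- 20% v 11%, n = 337: SE0 = √(2 x 0.155 x 0.845/337) = 0.02788; SE1 = √(0.2579/337) = 0.02766; (0.09 - 0.05464)/0.02766 = 1.278; power 89.9%.

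These are the stated 80% and 90%, obtained with one look.

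**3. The pairing in Section 12.3.1.** By the same method, 20% v 11% needs about 253 per group for 80% power and about 338 for 90%. So 337 is the 80% figure for 15.5% v 8.5%. The allowance for the other drugs' effects is already inside 337 and is not part of the step from 337 to 1,124.

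**4. Power with the Table 2 looks.** Information fractions are 62/1,124, 386/1,124, 774/1,124 and 1. The drift is the value that gives the fixed-design power: 1.96 + 0.841 = 2.80 and 1.96 + 1.278 = 3.24. Numerical integration of the joint distribution, confirmed by simulation with 1,000,000 runs, gives:

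| 337 evaluable per group | 15.5% v 8.5% | 20% v 11% |
|---|---|---|
| Single look | 80.0% | 89.9% |
| Efficacy and harm boundaries | 79.4% | 89.5% |
| Efficacy, and futility obeyed at every look | 76.6% | 87.3% |

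Other conventions for the drift move the last row within 76.4-76.9% and 87.1-87.6%.

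Keeping 80% needs a further factor of about 1.015 with efficacy boundaries only (337 x 1.015/0.90 = 380 enrolled per group, 1,140 in total). If futility is always obeyed the factor is about 1.09 (408 per group, about 1,224 in total).

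**5. Metformin.** The table's total row gives 563 v 561; 561 x 0.90 is about 505 evaluable per group.
- All three drugs effective: (20 + 11 + 11)/3 = 14.0% v (11 + 6 + 6)/3 = 7.67%; 90.1% with a single look, 87.4% with futility obeyed.
- Only metformin effective: 20% v 11%; 97.8% and 96.6%.

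**6. Updated size.** 225 per arm gives 450 per comparison group, and 450 x 0.90 = 405 evaluable. At the original rates, and with Table 2 as a stand-in for the recalculated boundaries, power is 86.2% and 94.2% with efficacy boundaries only, or 83.7% and 92.4% with futility always obeyed.

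**The case against.** The strongest reply is that the shortfall is about half a point. Section 12.4.2 makes futility advisory, so only the efficacy and harm boundaries are rules, and 79.4% and 89.5% are practically the stated figures. This stands. A reader might infer that the plan's own boundaries cut power to 77% and 87%, or that the inflation should have been about 1.21 (1.09/0.90). The protocol does not support that without the added condition that the futility line is followed every time.

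Second, the sentence promising at least 80% concerns metformin, and that promise holds in every case calculated. This stands too. The misnamed basis errs on the safe side, because the smaller comparison set the size. It remains misnamed.

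Third, 1,124 has been superseded by 1,350, which has a basis of its own: a 35% relative reduction with a projected control rate. A reader might infer that the current trial is underpowered; the figures for 405 evaluable per group give no support for this at the original rates. But Section 12.3 and Table 2 remain current text in version 3.4.

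Fourth, the 11% might mean 10% added for losses and about 1% spare (337 x 1.10 = 371, against 337 x 1.11 = 374). Adding 10% does not offset a 10% loss, since 371 x 0.90 = 334, and the spare 1% is below the 1.5% that even the efficacy looks need.

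Finally, Section 12.3 notes that covariate adjustment may raise power. It may, but the protocol does not quantify this, and it is not an allowance for interim looks.

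**Conclusion.** The point holds as a correction to the sample size text. The 10% loss takes the whole 11%, so Sections 12.3 and 12.3.1 are wrong to say that the interim plan is covered. The 80% and 90% are single-look powers for fluvoxamine or ivermectin. With monitoring, the cost is about half a point under the binding boundaries and about 2.5 to 3.5 points if futility is always obeyed. Section 12.3.1 also pairs 337 with the wrong power for 20% v 11%.

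This rests on the protocol's event rates, a 10% loss, an unadjusted comparison of proportions, and looks at the fractions in Table 2 applied equally to each drug's comparison. The figures for 1,350 are approximate, because neither the recalculated boundaries nor the projected control rate is given. Nothing here shows that the trial, at either size, fails its promise for metformin.

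**What to change.** Amend the wording of Sections 12.3 and 12.3.1:

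- State that the 11% covers losses only.
- Name fluvoxamine and ivermectin as the comparisons that set 337 per group, and give metformin's own power (about 505 evaluable per group).
- Report power under Table 2 both ways: about 79.4% and 89.5% without futility stopping, and about 77% and 87% if the futility boundary is always followed.
- Correct the pairing in Section 12.3.1: 337 per group gives 80% power for 15.5% v 8.5% and about 90% for 20% v 11%, for which 80% needs about 253.
- Mark the 1,124 calculation as the original design, and give the corresponding monitored power for 1,350 with its recalculated boundaries.

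The cost is protocol text and one power run by the statisticians. No patients are added and the design does not change. The quoted powers become slightly less favourable, and the futility case has to be shown openly.

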# Factorial design maximizes the use of placebo

Each patient gets 2 types of pills		Metformin (n=563)	Placebo (n=187)	
	Fluvoxamine (n = 375)	Metformin / Fluvoxamine n =188 6% event rate if both effective	Fluvoxamine / placebo n=187 11% event rate	
	Ivermectin (n=375)	Metformin/Ivermectin n = 188 6% event rate if both effective	Ivermectin/Placebo n = 187 11% event rate	
		Metformin / placebo n = 187 11% event rate	Placebo / Placebo n=187 20% event rate	
	Total	563	561	

[figure not shown]
• If two medications are effective, we will have 80% power to detect a difference over placebo.

• If only one medication is effective, we will have 90% power to detect a difference over placebo.

• Assumes a 10% loss to follow-up rate.

These considerations result in a planned enrollment of 1,124 participants (187-188 in each arm). Because these sample size calculations are based on marginal tests, the actual power may be higher when based on the planned tests using adjusted logistic regression models adjusted for various predictive factors as described later.

VERSION 3.4

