### VERSION 3.4

\*Updated sample size: 225 per arm, 1,350 total.

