#### 6.4 Number of Participants

Enrollment will occur remotely via the previously described methods for interested participants presenting to one of the PCR-testing sites or via self-referral to the study. Patients in assisted

living facilities do qualify for this study. The total number at each site will be affected by local incidence rates at the time of enrollment. We anticipate that at least 100 participants will be enrolled at each participating institution.

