#### Prespecified analyses:

A detailed SAP will be submitted to the DSMB and updated if needed prior to analyses. The primary efficacy analysis for each study drug, metformin, fluvoxamine, and ivermectin, will be based on a logistic regression model with a main effect for the relevant drug controlling for study site, and use of the other study drugs. In particular, no interaction effects will be included in this analysis. Prespecified subgroup analyses

include: pregnant women, and individuals who have already received a SARS-CoV-2 vaccine.

The SAP includes a sample-size re-calculation procedure that was pre-specified for the analysis of futility and efficacy on the first 2/3 of participants enrolled. This procedure was presented to and approved by the DSMB at the DSMB analysis of futility and efficacy done after 2/3 of participants were enrolled, + 14 days of follow-up. The updated total sample size for the study based on this sample size re-calculation is 1,350. This re-estimation accounts for a larger portion of participants being vaccinated and greater prevalence of monocloncal antibody use after enrollment than was envisioned when the protocol was written in fall 2020, and the resultant impact on the event rate in the placebo control arm; and external evidence from the Together Trial indicating a 33% relative reduction from fluvoxamine for which the original sample size would not provide adequate power. The updated sample size is expected to provide 80% power to detect a 35% relative reduction from fluvoxamine, and similarly for ivermectin, while accounting for the recent impact of vaccination and therapeutics by using a projected estimate of the event rate for the primary outcome in the participants randomized to the placebo control arm.

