### UNIVERSITY OF MINNESOTA 08December2021 COVID-OUT (formerly called MET-COVID) (MET29324)

follow a modified intent to treat (mITT) principle, excluding participants who were postrandomization screen failures and who did not ingest any study drug. Formal comparisons will use 2-sided tests with a 5% significance level.

Descriptive statistics will be reported for baseline covariate information. Continuous variables will be summarized using mean and standard deviations, as well as median and interquartile range for skewed variables. Binary and categorical variables will be summarized using counts and percentages. Differences in important prognostic variables will be monitored visually with formal statistical testing undertaken only at the request of the DSMB.

Each study drug version control comparison will be separate. Each control group will consist of the participants who were eligible to receive the study drug but were assigned to a relevant placebo control arm instead. The metformin comparison will control for fluvoxamine and ivermectin use, and the fluvoxamine and ivermectin versus control comparisons will each control for metformin use. Primary hypotheses will be evaluated using logistic regression with a main effect for the relevant drug adjusted for study site and use of the other study drugs. The statistical significance of the main effect will be evaluated using a likelihood ratio test with interim monitoring boundaries specified above.

A secondary analysis for each study drug versus control comparison will control for age and BMI as well. Metformin effect heterogeneity with respect to biologic sex will be assessed in both cohorts though a logistic regression model with an interaction term, as well as separate logistic regression models fit to the data from males and females. During interim analyses, some participants will not have been followed adequately long for inclusion in the primary analysis. As a secondary analysis, marginal cumulative incidence rates in each arm at the specified follow-up interval will be estimated using the Kaplan-Meier method by censoring those in the midst of follow-up who have yet to experience the primary endpoint at their point of last study contact.

Laboratory outcomes, which are continuous longitudinally measured outcome, will be evaluated using generalized estimating equations with a treatment effect and adjustments for the corresponding outcome at baseline.

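### Section 12.3 says adjustment for predictive factors may raise power, but the primary model adjusts only for site and the other study drugs; adding age, BMI and vaccination is a cheap improvement

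*Protocol*

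**What the plan says.** - **Power remark.** Section 12.3, below the factorial table, derives 1,124 participants from marginal tests and adds that "the actual power may be higher when based on the planned tests using adjusted logistic regression models adjusted for various predictive factors as described later". It gives no figure and does not say which of the planned tests it means.
- **Primary model.** The paragraph headed Prespecified analyses, after Section 12.3.1, fixes a "logistic regression model with a main effect for the relevant drug controlling for study site, and use of the other study drugs". Data Analysis (the second section numbered 12.2) repeats it: "logistic regression with a main effect for the relevant drug adjusted for study site and use of the other study drugs", tested by likelihood ratio.
- **Age and BMI.** Data Analysis adds: "A secondary analysis for each study drug versus control comparison will control for age and BMI as well".
- **Vaccination.** The prespecified subgroups include "individuals who have already received a SARS-CoV-2 vaccine". The same paragraph says of the larger sample size: "This re-estimation accounts for a larger portion of participants being vaccinated", and links this to the placebo event rate. The new size is in Section 5.1: "Updated sample size: 225 per arm, 1,350 total".
- **Other prognostic information.** Data Analysis allows for it, but only for secondary outcomes.
- **Randomization.** Section 12.1 stratifies by site, with separate schedules for each pattern of drug eligibility. Vaccination, age and BMI play no part.

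**The concern.** The power remark sits inside the sample size argument for the primary hypotheses, so a reader will look to the primary model for the predictive factors. That model contains only site and co-assigned drug. The patient-level factors that the protocol names elsewhere are all outside it, including vaccination, which it treats as changing the event rate.

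Two things are at stake. The protocol suggests a power reserve that the primary test may hardly have. And the test makes no use of baseline information that is already on the data list: age and BMI serve for eligibility, and vaccination is needed for a planned subgroup.

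**Working it through.** **1. The plan's own figure.** Pooled-variance formula, two-sided 5%, p̄ the mean of the two rates:

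n = [1.96·√(2p̄(1−p̄)) + z·√(p₁(1−p₁)+p₂(1−p₂))]² / (p₁−p₂)², with z = 0.842 for 80% power and 1.282 for 90%.

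- Both drugs effective, arm rates 20/11/11/6%: the margins are (20+11)/2 = 15.5% and (11+6)/2 = 8.5%. At 80% power n = (0.901+0.385)²/0.07² ≈ 337.1, so 338.
- One drug effective, 20% vs 11%, 90% power: n = (1.003+0.651)²/0.09² ≈ 337.7, so 338.

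The protocol's 337 per group is reproduced without any covariate adjustment, and 337 × 1.11 ≈ 374 is two arms of 187. (Section 12.3.1 ties 337 to 20% vs 11% at 80% power, where this formula gives 253. That is a separate matter.)

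**2. What the primary adjustment adds at the original size.** Simulated likelihood ratio tests, 338 per group, rates 20/11/11/6%, 20,000 trials per row. Site effects are not in the protocol, so the between-site log-odds SD is assumed. The protocol says "We anticipate that at least 100 participants will be enrolled at each participating institution", which caps the number of sites at 11 for 1,124; six is also tried.

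| Sites, SD | Marginal | + other drug | + site |
|---|---|---|---|
| 6, 0 | 80.7% | 81.2% | 81.0% |
| 6, 0.3 | 80.6% | 81.0% | 81.3% |
| 6, 0.6 | 80.3% | 80.6% | 81.8% |
| 11, 0.3 | 80.9% | 81.3% | 81.4% |
| 11, 0.6 | 80.4% | 80.8% | 82.2% |

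The total gain is 0.3 to 1.8 points. A separate run (337 per group, 6 sites, 4,000 trials) took the SD further. At SD 0, 0.3, 0.5, 0.8 and 1.0 the gain was 0.0, −0.1, 1.3, 2.6 and 3.7 points with both drugs effective, and 0.1, 0.4, 1.0, 1.4 and 2.2 with one.

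**3. What age, BMI and vaccination would add at the updated size.** Two arms give 2 × 225 = 450 per group, or 405 after 10% loss. Metformin has 3 × 225 × 0.9 ≈ 607. The relative reduction is 35%. The projected control rate is not stated, so 19.6% and 21.4% were chosen to give 80% power by formula at 450 and 405; 20% was also tried. Also assumed: 50% vaccinated; modest effects (odds ratio 0.5 for vaccination, 1.3 per SD of age, 1.2 per SD of BMI); strong effects (0.33, 1.6, 1.4).

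| Per group, control rate | Modest: current → expanded | Strong: current → expanded |
|---|---|---|
| 450, 19.6% | 80.7 → 81.8% | 80.6 → 83.7% |
| 405, 21.4% | 80.9 → 81.9% | 80.7 → 83.7% |
| 405, second independent run | 80.8 → 82.2% | 79.7 → 83.6% |
| 405, 20% | 77.1 → 78.2% | 77.1 → 80.5% |
| 405, 21.4%, 20% of vaccination status missing and imputed | 80.2 → 81.3% | 79.6 → 82.5% |
| 607, 20% (metformin) | 91.0 → 91.5% | 90.9 → 92.9% |

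With no prognostic value (405, 21.4%), power goes from 80.6% to 80.4%.

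**4. Chance imbalance in vaccination.** With half vaccinated, the SD of the between-group difference is √(0.5/405) = 3.5 points, or √(0.5/450) = 3.3. An imbalance of 5 points or more in either direction then occurs in about 15% or 13% of trials. At 405 per group and 21.4%:

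- Against the drug: power is 73.0% (current) vs 80.8% (expanded) with modest effects, and 71.3% vs 84.0% with strong.
- In the drug's favour: one-sided error at 1.96 is 4.0% vs 2.4% with modest effects, and 5.6% vs 3.0% with strong.
- Both directions, unadjusted two-proportion test, vaccination odds ratio 0.5 / 0.33: error is 4.5% / 5.5% when the imbalance favours the drug, 1.4% / 0.8% when it goes against it, and 2.5% overall in both cases.

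**5. Changing the final statistic after the interim.** Spending the remaining alpha at 1,350 after the Table 2 efficacy bounds gives a final bound of 2.026. In 60,000 null trials (18% event rate assumed; looks at 386 and 774; the look at 62 left out, nominal error 0.009%), one-sided error was 2.55% with the current final model and 2.60% with the expanded one (modest effects), and 2.54% vs 2.70% (strong), SE 0.07 points.

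**The case against.** The sentence in Section 12.3 can be read as literally true. It is hedged and refers to planned tests in general. Site and co-assigned drug are predictive: the factorial table has the second drug moving the rate from 20% to 11% and from 11% to 6%. An age- and BMI-adjusted analysis is also described later, for every drug. All of this stands, and it is why the sentence is overstated and not wrong.

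Adjusting the primary test only for the stratification factor and the co-treatment is also a legitimate prespecified choice. Changing it after the two-thirds interim brings in a final statistic other than the one monitored, and vaccination is collected only where available. These are real costs and limit the point to an improvement. The statistical analysis plan was not available, but the protocol itself fixes the primary model, so the point does not depend on detail left to that plan.

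Three stronger readings are not supported:

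- A reader might infer that the sample size leans on the suggested gain. It does not: 337 follows from the marginal formula, and the gain was not used to reduce it. The re-estimation to 1,350 claims no gain from adjustment.
- A reader might infer that the current primary test is too liberal. That holds only if trials with a favourable imbalance are singled out. Under the opposite imbalance the error is well below nominal, and overall it is about 2.5%.
- A reader might take 0 to 2 points as a property of the design. It rests on an assumed site effect.

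**Conclusion.** The point holds as an overstated sentence and a low-cost opportunity to improve the primary analysis. No stated power, alpha or sample size is wrong because of it.

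The primary adjustment is worth about 0 to 2 points of power for a between-site log-odds SD up to 0.6, and up to about 4 at SD 1.0. The protocol gives no site effect with which to narrow this.

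For fluvoxamine and ivermectin, the covariates outside the model would add about 1 to 4 points. For metformin, whose power is already about 91% under these assumptions, they would add about 0.5 to 2. These figures depend on assumed covariate odds ratios, 50% vaccinated and assumed control rates. The other benefit is a result less sensitive to chance vaccination imbalance in either direction. Control of overall type I error is not an argument for the change.

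**What to change.** **Preferred.** While still blinded and before final unblinding, the blinded statistician amends the primary model for each drug to: *logistic regression with a main effect for the relevant drug, adjusted for study site, use of the other study drugs, age, BMI and SARS-CoV-2 vaccination status at enrolment*.

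- Keep the likelihood ratio test, and impute missing vaccination status by the method in the Missing Data section.
- Report the present site-and-drug model as a sensitivity analysis.
- Record that the change was made blind. Section 12.0 and Data Analysis already give the blinded statistician authority to amend the analysis plan.
- Confirm type I error at the trial's actual looks, with the boundary recalculated as in Section 12.4.2. In the simulation above the excess over 2.5% was at most about 0.2 points.

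**Cost.** One sentence in the protocol and analysis plan, and no new data items. The downsides are a more conditional odds ratio, some imputation, and a final statistic that differs from the one used at the completed interim.

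**If the model is not changed.** Reword the remark in Section 12.3 to say that the primary test adjusts only for study site and the other study drugs, and that little gain in power is expected from this. That costs nothing.
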